	§ Breast cancer history				
	§ Breast cancer liver metastasis verified by biopsy				
	§ Patient amendable for liver surgery and pre- and				
	postoperative oncological treatment				
	§ Previous or present non-skeletal extrahepatic disease				
Exclusion Criteria:	§ Pregnancy				
	§ > 4 liver metastases on preoperative or previous				
	examination				
	§ Progression of disease upon oncological treatment				
Study Schedule:	First-Subject-In is planned in 2020				
	Last-Subject-In is planned for 2026				
	Last-Subject out is planned for 2029				
Ethics approval	Sweden. Dnr 2018-116-31M and 2019-05717				
Web	https://www.umu.se/en/research/projects/the-breclim-trial/				

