## Material: Patient selection

Inclusion will start in all six regional cancer centres in Sweden.

Inclusion criteria	
 
§ Signed informed consent
 
§ >18 years old
 
§ ECOG 0-1
 
§ Breast cancer history
 
§ Breast cancer liver metastasis verified by biopsy
 
§ Patient amendable for liver surgery and pre- and postoperative oncological treatment
 
§ 1-4 liver metastasis amendable to surgery with functional liver remnant volume >30%
 

Exclusion criteria	
 
§ Previous or present non-skeletal extrahepatic disease
 
§ > 4 liver metastases on preoperative or previous examination
 
§ Pregnancy
 
§ Progression of disease upon oncological treatment
 

Participants will be randomized by an oncologist at a study centre. Participants will be stratified on study centre. Randomization and stratification will be computer-based and administered upon the study website. The 1:1 allocation of participants into groups will be performed in random blocks, with random block sizes of 2 to 6. The study website will apply the Pheedit system and provide electronic CRFs. Each site coordinator will have access to the website and will be able to include and randomize participants. Non-participants who fulfill inclusion criteria will be registered by date, initials, clinic and date of birth.

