### Estimated sample size and power

Based on preliminary results from a nationwide retrospective study (7) and the most recent case series, we assume that the overall 3-year survival to be approximate 40% averaged across both groups. Mariani et al (5) conducted a case control study of a population similar to the inclusion criteria in this study and detected RR 3.04 (CI: 1.87-4.92) in a multivariate cox regression analysis in favour of liver surgery. A smaller reduction of risk is clinically relevant but the challenge of this study is to recruit participants. In order to reach a power of 80 % to detect a hazard ratio of 1.9 with a significance level of 0.05, 190 study participants are required. Under the assumption of a drop-out rate of 5%, we therefore intend to include 200 participants in total. The sample size calculation is made assuming an unadjusted analysis. In the analysis of the primary outcome, model adjustments for baseline covariates will be made (age, molecular subtype of primary tumour, TNM-stage of primary tumour, disease free interval, single or multiple BCLM and presence of bone metastases yes/no). As these covariates are well known prognostic factors, we expect this to give additional gain in power or equivalent opportunity to detect smaller hazard ratios (8). Based on results from a nationwide retrospective study (7) and the most recent case series we assume that the secondary endpoint 3-years survival will be 30% in the control arm (oncological treatment only) and 50% in the treatment arm (surgery and oncological treatment). To reach 80% power with a 5% drop out rate and a level of significance p<0.05, the total study population is calculated to 200 participants also in this analysis.

Isolated oligometastases in the liver affect about 5% of those with advanced breast cancer. This corresponds to 70 patients per year in Sweden. We assume that we can include 50% of these, thus 35 per year. The study will be open for recruitment from centres outside of Sweden with a further specified protocol for surgical and oncological treatment and additional ethical review.

The study will be open for recruitment during 8 years and participants will be followed for at least 3 years. Interim analyses will be performed by the safety committee after inclusion of 100 participants. If the primary endpoint is reached at the interim analysis, the study will be

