### **Statistical methods**

The primary outcome, time to death for any cause, will be visualized in a Kaplan-Meier plot and analyzed using Cox proportional hazard regression. The null hypothesis to be tested is that the hazard for the intervention group is equal to the hazard of the control group, in a twosided test. A random effects model will be applied with study centre as random effect. Adjustments will be made for age, molecular subtype of primary tumour, TNM-stage of primary tumour, disease free interval, single or multiple BCLM and presence of bone metastases (yes/no) for the purpose of increasing precision and statistical power in analysis. Age will be modelled as a continuous variable using natural cubic splines with three nodes distributed at the 10th, 50th and 90th percentile of the age distribution to account for nonlinear effect. The significance level will be set at 0.05.

Three years survival will be analyzed using logistic regression, adjusted for the same covariates as above,

Progression free survival and breast cancer specific survival will be analyzed using cox regression, as described for the primary outcome.

Predictive factors for survival will be analyzed in a cox proportional hazards model. Quality of life will be analyzed using a ordinal proportional odds regression model.

[name] and statistician at Registercentrum Norr, will be responsible for the statistical analysis plan.

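### The logistic regression fixed for three-year survival cannot use participants censored alive before 36 months; the bias is small if the trial runs to plan and larger if follow-up is unequal or cut short

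*Protocol*

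**What the plan says.** Under Statistical methods, the primary outcome gets a Kaplan-Meier plot and Cox regression, and progression-free and breast cancer specific survival also get Cox regression. Three-year survival is treated differently: "Three years survival will be analyzed using logistic regression, adjusted for the same covariates as above".

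Estimated sample size and power gives this endpoint its own calculation, with assumed three-year survival of 30% in the control arm and 50% in the local treatment arm: "To reach 80% power with a 5% drop out rate and a level of significance p<0.05, the total study population is calculated to 200 participants". The same section plans an interim analysis after 100 inclusions, assumes 35 inclusions per year, and says that the study stops if the primary endpoint is reached at the interim.

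On follow-up, that section states: "The study will be open for recruitment during 8 years and participants will be followed for at least 3 years". The Time plan also gives up to 8 years of recruitment, from January 2020. The synopsis has the last participant entering in 2026 and adds: "Last-Subject out is planned for 2029". Under Variables and measures, survival is to be evaluated primarily by intention to treat.

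**The concern.** A plain logistic model needs a yes or no at 36 months. A participant last known alive at, say, 20 months has no value for it and must be excluded, counted as alive, or imputed. Exclusion is selective. A participant who dies at 20 months stays in as a death, while one censored alive at 20 months disappears. Three-year survival is then underestimated in both arms, and the contrast shifts if censoring differs between arms. Excluding randomised participants also sits badly with the intention-to-treat aim.

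This is a choice of method written into the protocol, not a detail left open for the analysis plan. It affects the only secondary endpoint that has its own sample size. The other survival comparisons in the same section use a method that handles censoring.

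**Working it through.** **Inputs from the protocol.** Three-year survival 30% and 50%; 80% power; significance level 0.05; 5% drop-out; 200 in total, allocated 1:1; 35 inclusions per year; interim at 100.

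**Assumptions added here.** A two-sided test (stated only for the primary outcome), exponential survival, exponential drop-out independent of survival within each arm, and uniform accrual.

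**1. The protocol's own figure.** For two proportions with pooled variance:

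n per arm = [1.96 × √(2 × 0.4 × 0.6) + 0.84 × √(0.3 × 0.7 + 0.5 × 0.5)]² / 0.2² ≈ 93, so 186 in total.

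Allowing for 5% drop-out, 186 / 0.95 = 195.8, or 196. The stated 200 is reproduced to within 3%.

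**2. Trial run to plan, 5% drop-out.** Yearly hazards are λ = −ln(0.3)/3 = 0.401 (control) and −ln(0.5)/3 = 0.231 (local treatment). The drop-out rate is γ = −ln(0.95)/3 = 0.0171.

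- Known alive at 36 months: S × 0.95.
- Known dead: λ/(λ+γ) × (1 − e^(−3(λ+γ))).
- Complete-case estimate: known alive / (known alive + known dead).

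| Arm | Known alive | Known dead | Unknown | Complete-case estimate |
|---|---|---|---|---|
| Control | 0.285 | 0.686 | 2.9% | 29.4% (true 30%) |
| Local treatment | 0.475 | 0.489 | 3.6% | 49.3% (true 50%) |

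The odds ratio is 2.34, against a true value of 2.33.

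Power with 100 randomised per arm, Kaplan-Meier using Greenwood's variance S²/n × λ/(λ+γ) × (e^(3(λ+γ)) − 1):

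| Drop-out | Complete-case binary analysis | Kaplan-Meier at 36 months |
|---|---|---|
| 5% | 82.6% | 82.8% |
| 10% | 81.2% | 81.6% |
| 20% | 77.9% | 78.9% |

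**3. Drop-out of 10% in one arm only** (an assumption; the protocol gives no figure by arm). The same formulas give:

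- control arm only: 28.7% against 50%, a difference of 21.3 points;
- local treatment arm only: 30% against 48.5%, a difference of 18.5 points.

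**4. Eight years of recruitment combined with close at the end of 2029.** Recruitment from January 2020 would end in December 2027. The 200/8 = 25 final-year entrants (12.5 per arm) would then have 2 to 3 years of follow-up. The share still alive at close is (e^(−2λ) − e^(−3λ))/λ, which is 36.9% in control and 56.2% in local treatment. That gives 12.5 × 0.369 + 12.5 × 0.562 = 4.6 + 7.0, or about 12 censored alive; the others are known deaths.

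Without any drop-out, the complete-case estimates become:

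- control: 87.5 × 0.30 / (100 − 4.6) = 27.5%;
- local treatment: 87.5 × 0.50 / (100 − 7.0) = 47.1%.

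The levels fall by almost 3 points, while the difference stays near 19.5 points.

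**5. Data cut at an interim stop.** At 35 per year, 100 inclusions take 100/35 = 2.86 years, so the longest possible follow-up is below 36 months. With T = 2.86, the expected share dead per arm is 1 − (1 − e^(−λT))/(λT). With 50 per arm this gives 20.2 deaths in control and 13.4 in local treatment: about 34 deaths and 66 censored alive. Every known 36-month outcome is a death, so the logistic model cannot be estimated. Kaplan-Meier would use all 100 participants, but only up to about 34 months; it could not give a 36-month value either.

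At an assumed slower 25 per year (4.0 years), about 41 would have died, 10 would be known alive at 36 months, and 49 would be censored earlier. The complete-case estimates would be 3.75/(3.75 + 24.45) = 13% for control and 6.25/(6.25 + 16.70) = 27% for local treatment. Kaplan-Meier at 36 months would be estimable there.

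**The case against.** The strongest reply is that the protocol intends 36-month status for everyone. It promises at least three years of follow-up, schedules a 36-month visit, and records vital status on an end-of-study form. For all-cause death with fixed follow-up, a binary analysis is a standard choice. The 200 already allows for 5% drop-out, and a censoring-aware analysis of the same deaths is the primary analysis. All of this stands, and it is why the point is minor. What remains is that the named method has no place for the drop-out that the protocol itself expects.

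Four stronger readings are tempting, and the document does not support them.

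- **Late entrants will lack 36 months.** This requires joining the 8-year recruitment of one section to the 2029 close of another, against the stated three-year minimum. Each calendar is consistent with three years when read alone. Even on the joined calendar, about 12 of the 25 final-year entrants are censored alive. Taking these 12 from 190 leaves about 178 and power of about 78%. A fall to about 167 and 76% would follow only if known deaths were discarded too.
- **An early stop makes the analysis impossible.** The protocol says that the study stops and controls may cross over. It does not say that follow-up ends or that data are cut at the 100th inclusion. If follow-up continues to 36 months, status is obtained; crossover would then affect any method equally.
- **The endpoint was sized on the wrong scale.** The model yields an adjusted odds ratio, while planning used 30% against 50%. Sizing on the log odds ratio gives 203 after drop-out, against 200 stated, so this shows no design error.
- **At least 10 participants will lack status.** The 5% is a planning assumption, not a floor, and some who drop out would have died by 36 months or have known vital status. The calculation gives 3% to 4% unknown per arm.

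How unknown status is handled may also be settled in an analysis plan not seen here. The point therefore concerns the method that the protocol fixes, not a missing rule.

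**Conclusion.** The concern holds as a minor point on a secondary endpoint. The fixed logistic model cannot use participants censored alive before 36 months, and leaving them out biases three-year survival downwards. If the trial runs to plan, the bias is under 1 point per arm and the power loss about 0.2 points. It matters more if drop-out differs between arms, if the two calendars were combined, or if data were cut at an interim stop; each of these is conditional, and none is what the protocol states will happen. The sizes rest on exponential survival and on drop-out that is independent of survival within each arm. If drop-out were related to prognosis, Kaplan-Meier would be biased as well. The sample size of 200 stands.

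**What to change.** Replace the sentence on three-year survival with wording such as: three-year survival is estimated in each arm by Kaplan-Meier at 36 months in all randomised participants, and the difference is reported with a 95% confidence interval; the covariate-adjusted comparison uses 36-month pseudo-observations with the same covariates as the primary analysis. Keep the logistic model as a sensitivity analysis.

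Two short clarifications would remove the conditional cases: state whether follow-up of vital status continues to 36 months after an interim stop, and reconcile the recruitment period and closing year between the synopsis, the sample size section and the Time plan. The first is needed whichever method is used, because no method gives a 36-month estimate when nobody has been followed that long.

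The cost is a change of wording and slightly more analysis work. It needs no further data or participants, and the required number does not change.

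### As worded, the logistic model for three-year survival leaves out study centre, the randomisation's stratification factor, which the main Cox models include; adding it is a free improvement.

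*Protocol*

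**What the plan says.** Protocol, Material: Patient selection, names one stratification factor: "Participants will be stratified on study centre". Allocation is blocked: "The 1:1 allocation of participants into groups will be performed in random blocks, with random block sizes of 2 to 6".

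Protocol, Statistical methods, builds the primary Cox model in two separate sentences. The first brings in centre: "A random effects model will be applied with study centre as random effect". The second lists the adjustments: "Adjustments will be made for age, molecular subtype of primary tumour, TNM-stage of primary tumour, disease free interval, single or multiple BCLM and presence of". The sixth item, where this quote breaks off, is bone metastases. Estimated sample size and power gives the same six variables and calls them baseline covariates: "model adjustments for baseline covariates will be made (age, molecular subtype of primary tumour, TNM-stage of primary tumour, disease free interval, single or multiple BCLM", again ending with bone metastases. Centre is in neither list.

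Two neighbouring sentences then specify secondary endpoints in different words:

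- Three-year survival: "Three years survival will be analyzed using logistic regression, adjusted for the same covariates as above".
- The other two survival endpoints: "Progression free survival and breast cancer specific survival will be analyzed using cox regression, as described for the primary outcome".

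**The concern.** The second of those sentences carries over the whole primary model, including the centre effect. The first carries over the covariates, a term that the protocol uses for the six variables and not for centre. A statistician who follows the text literally would fit a logistic model without the factor that the randomisation was stratified on.

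Stratified allocation makes the arms alike within each centre. If centre also predicts survival, a model without it does not use that balance: the standard error is too large for the design, the test rejects too rarely under the null, and power is lost. Centre differences are plausible here, because local treatment follows each centre's own routine (Local treatment) and recruitment may open to centres outside Sweden (Estimated sample size and power). Three-year survival is also the only secondary endpoint for which the protocol gives its own power statement.

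**Working it through.** **1. The plan's own figure.** Inputs from Estimated sample size and power: three-year survival 30% against 50%, 80% power, level 0.05, 5% drop-out, total 200. The two-sided level is stated for the primary test and assumed here. With pooled variance and no continuity correction,

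n per arm = [1.960·√(2·0.40·0.60) + 0.842·√(0.30·0.70 + 0.50·0.50)]² / 0.20² = (1.358 + 0.571)² / 0.04 ≈ 93.

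That is 186 in total, and 186/0.95 = 195.8, so 196. The stated 200 is reproduced to rounding. The formula uses neither centre nor covariates, so the sample size does not depend on this point.

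**2. What is assumed.** The protocol gives no between-centre variation. It is represented by a normal centre effect with standard deviation SD on the logit scale. Around a survival of 40%, centres one SD below and above the average would have:

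| SD | one SD below | one SD above |
|---|---|---|
| 0.3 | 33% | 47% |
| 0.5 | 29% | 52% |
| 0.8 | 23% | 60% |
| 1.0 | 20% | 64% |

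**3. Simulation with and without centre.** N = 190, six centres of assumed unequal size, permuted blocks of 2, 4 or 6 within centre, 3000 runs per setting, logistic Wald test. The true log odds ratio in the power runs is ln[(0.5/0.5)/(0.3/0.7)] = 0.847. The six covariates were not simulated, and centre entered as fixed terms.

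| SD | Type I error, without / with centre | Power, without / with centre | Gap in power (points) |
|---|---|---|---|
| 0 | 4.8% / 5.0% | 79.9% / 80.9% | 1.0 |
| 0.3 | 5.0% / 5.4% | 79.6% / 80.7% | 1.1 |
| 0.5 | 4.4% / 5.1% | 77.9% / 79.7% | 1.8 |
| 0.8 | 4.0% / 5.5% | 70.8% / 74.8% | 4.0 |
| 1.0 | 3.4% / 5.4% | 66.9% / 73.7% | 6.8 |

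Monte Carlo standard errors are √(0.05·0.95/3000) = 0.4 points for type I error and √(0.8·0.2/3000) = 0.7 points for power. Power falls with SD in both columns because 30% and 50% hold only for the average centre. The effect of omitting centre is the gap between the two models in a row.

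**4. How much of the gap is real.** With SD 0 there is nothing to gain, yet the fixed-term model shows 1.0 point, and its type I error runs slightly above 5% in most rows. Subtracting that 1.0 leaves 0.1, 0.8, 3.0 and 5.8 points at SD 0.3, 0.5, 0.8 and 1.0. A separate check used a centre-stratified test that holds its size (type I error 4.8% to 5.2%). Against that test, omitting centre costs 1.7, 3.6 and 5.7 points of power at SD 0.5, 0.8 and 1.0, and nothing at SD 0. Type I error without centre was 4.5%, 3.7% and 3.4% at those three SDs. The loss is therefore not merely an artefact of fixed terms.

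**5. With the covariates in the model.** A further simulation included six covariates (12 parameters plus treatment) and a conditional odds ratio of 2.6. At SD 0.6 it gave 4.3% type I error and 81% power without centre, against 5.4% and 83% with fixed centre terms. The direction is the same and the size similar.

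**6. The odds ratio.** At SD 0.8 the median log odds ratio was 0.765 without centre and 0.864 with it, that is odds ratios of e^0.765 = 2.15 and e^0.864 = 2.37, against a centre-conditional truth of 2.33.

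**The case against.** The strongest reply is that the omission is inferred. The three-year sentence ends on a comma and may be unfinished, nothing in it excludes centre, and the paragraph it points back to contains both the centre effect and the covariate list. A reader might infer that the sponsor decided to drop centre; the text does not show that. What stands against the reply is the consistent usage: both covariate lists omit centre, and the neighbouring sentence uses wider wording. The literal reading is the better one, but it is not certain.

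A second reply is that a centre term is a detail for the statistical analysis plan. That would hold if the protocol were silent. It names both the method and the adjustment set for this endpoint, so the remark concerns what is written.

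A third reply is that the gain is small and partly an artefact, and that a random intercept, the natural remedy, was not itself simulated. This is right as far as it goes. At an SD of 0.3 almost nothing is lost, and the figures for fixed terms and for the stratified test are only a guide to a random intercept.

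Three stronger readings are tempting and are not supported:

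- That leaving out centre inflates the false-positive rate. The test becomes conservative.
- That the odds ratio is biased. Under randomisation the shift towards 1 is non-collapsibility: an odds ratio averaged over centres is a different quantity from one conditional on centre.
- That every Cox model in the protocol includes centre. It is stated for the primary endpoint and carried over to progression-free and breast cancer specific survival. It is not stated for the predictive-factor model, and the ordinal quality-of-life model names no centre term either.

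**Conclusion.** The point holds on a literal reading, as a free improvement and not as an error that threatens a conclusion. The stated logistic model for three-year survival lacks the only stratification factor named for the randomisation, while the models for the three other survival endpoints named above include it. The cost is a conservative test and lost power: nothing if centres do not differ, under 1 to about 2 points for a centre SD up to 0.5, and about 4 to 7 points at 0.8 to 1.0. These sizes rest on assumed centre variation, assumed centre sizes and, for the main table, a model without the six covariates. The primary analysis and the total of 200 are unaffected.

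**What to change.** Complete the sentence in Statistical methods, for example: *Three-year survival will be analysed by logistic regression with the six covariates listed for the primary outcome and a random intercept for study centre.* If another estimator is chosen for the 36-month comparison, keep centre in it.

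A random intercept matches the primary model and spends fewer parameters than five fixed centre terms. That matters because 40% survival among 190 participants gives only about 76 survivors to support a model that already carries the six covariates.

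The cost is a few words. Centre is already recorded for every participant and the sample size stays as it is. Settling the wording before outcome data are compared by arm also removes a later choice between two models.
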